4.3. Protocol Deviations

A listing will be provided for all randomized subjects who violated at least 1 inclusion or exclusion criterion. The listing will include the criteria not met. A listing of subjects who received the wrong study drug will also be provided.

4.4. Missing Protocol-Specified Information due to COVID-19

An overall summary of the number and percentage of subjects with missed or virtual visits (e.g., at least 1, with 1, 2, 3 or more visits) due to the COVID-19 pandemic will be provided. The denominator for the percentage calculation will be the total number of subjects in the all B/F/TAF analysis set.

A by-subject listing of subjects with missed or virtual visits due to COVID-19 will be provided by subject ID number in ascending order.

The determination of missing or virtual Visits due to COVID-19 was done using Natural Language Processing (NLP) to search the CRF comment fields. A detailed explanation of the algorithm is given in [Appendix 5](#).

5. BASELINE CHARACTERISTICS

5.1. Demographics and Baseline Characteristics

Subject demographic data (eg, age, sex at birth, race, and ethnicity) and baseline characteristics (eg, body weight, height, and body mass index [BMI]) will be summarized by treatment group and overall using descriptive statistics (n, mean, SD, median, Q1, Q3, minimum, and maximum) for continuous data and by the number and percentage of subjects for categorical data. The summaries of demographic data and baseline characteristics will be provided by treatment groups for subjects in the All B/F/TAF Analysis Set (noticing that the baseline for all B/F/TAF analysis will be adjusted based on first dose of B/F/TAF), respectively.

No statistical comparisons will be made for the All B/F/TAF analysis.

5.2. Baseline Disease Characteristics

The following baseline disease characteristics will be summarized by treatment group and overall using descriptive statistics for subjects in All B/F/TAF A:

- HIV-1 RNA (\log_{10} copies/mL)
- HIV-1 RNA categories (copies/mL): (a) $\leq 100,000$, (b) $> 100,000$ to $\leq 400,000$, and (c) $> 400,000$
- CD4+ cell count (/ μ L)
- CD4+ cell count categories (/ μ L): (a) < 50 , (b) ≥ 50 to < 200 , (c) ≥ 200 to < 350 , (d) ≥ 350 to < 500 , and (e) ≥ 500
- CD4 percentage (%)
- Mode of infection (HIV risk factors)
- HIV disease status
- eGFR_{CG} (mL/min)
- HIV/HBV coinfection status (Yes/No/Missing, see Section 9.1 for definition)
- HIV/HCV coinfection status (Yes/No/Missing, see Section 9.2 for definition)

No statistical comparisons will be made for the all B/F/TAF analysis.

5.3. Medical History

General medical history data will be collected at screening and listed only. General medical history data will be coded using the current version of Medical Dictionary for Regulatory Activities (MedDRA).

6. EFFICACY ANALYSES

All necessary summaries on the primary efficacy endpoint (at Week 48) and the secondary endpoints at Weeks 48, 96 and 144 have been performed as part of the Week 48 CSR, Week 96 CSR, Week 144 CSR and will not be repeated for the final analysis.

6.1. Primary Efficacy Endpoint

The primary efficacy endpoint is the proportion of subjects with HIV-1 RNA < 50 copies/mL at Week 48 as determined by the US FDA-defined snapshot algorithm {[U. S. Department of Health and Human Services 2015](#)}. The proportions are expressed as percentages for presentation purposes.

The statistical analysis methods for the primary efficacy endpoint were described in the Week 48 SAP and the analysis was performed in the Week 48 analysis.

6.2. Secondary Efficacy Endpoints

6.2.1. Definition of the Secondary Efficacy Endpoints

The secondary efficacy endpoints include:

- The proportion of subjects with HIV-1 RNA < 50 copies/mL at Weeks 96 and 144 as determined by the US FDA-defined snapshot algorithm
- The proportion of subjects with HIV-1 RNA < 20 copies/mL at Weeks 48, 96, and 144 as determined by the US FDA-defined snapshot algorithm
- The change from baseline in \log_{10} HIV-1 RNA and CD4+ cell count at Weeks 48, 96, and 144
- The proportion of subjects who achieve HIV-1 RNA < 50 copies/mL at OL Week 48 and OL Week 96 as defined by Missing = Excluded and Missing = Failure algorithm
- The change from baseline in CD4+ cell count at OL Weeks 48 and 96.

The statistical analysis methods for the secondary efficacy endpoints at Weeks 48, 96, and 144 (based on data included in the randomized phase analysis) and at Week 48 OL (based on data included in the All B/F/TAF analysis) were described in the previous interim analyses SAPs or programming specification, and the analyses were performed in the previous interim analyses. In this final analysis, the last 2 secondary endpoints will be analyzed for all visits with details defined in the next section (Section 6.3).

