The proportion of subjects who achieve HIV-1 RNA < 50 copies/mL at Weeks 96 and 144 and the proportion of subjects who achieve HIV-1 RNA < 20 copies/mL at Weeks 48, 96, and 144 as defined by the US FDA-defined snapshot algorithm will also be summarized. The 95% CIs will be constructed in the same manner as described for the primary efficacy endpoint.

The change from baseline in \log_{10} HIV-1 RNA and CD4+ cell count at Weeks 48, 96, and 144 will be summarized using descriptive statistics. The differences and the associated 2-sided 95% CIs will be constructed using an Analysis of Variance (ANOVA) model, including treatment (GS-9883/F/TAF vs. DTG + F/TAF), baseline HIV-1 RNA level ($\leq 100,000$ copies/mL vs. $> 100,000$ copies/mL), and region (US vs. Ex-US) as fixed effects in the model.

The proportion of subjects who achieve HIV-1 RNA < 50 copies/mL at Weeks 48 OL and 96 OL will be summarized, where missing HIV-1 RNA will be excluded and treated as failure, respectively. The changes from baseline in CD4+ cell count and percentage at Weeks 48 OL and 96 OL will be summarized using descriptive statistics.

Adverse events, clinical laboratory assessments, and pharmacokinetic parameters will be summarized using descriptive statistics.

A total of approximately 600 HIV-1 infected subjects, randomized in a 1:1 ratio to 2 treatment groups (300 subjects per treatment group), achieves at least 95% power to detect a non-inferiority margin of 12% in Week 48 response rate (HIV-1 RNA < 50 copies/mL as defined by the US FDA-defined snapshot algorithm) difference between the 2 treatment groups. For the sample size and power computation, it is assumed that both treatment groups have a response rate of 91% (based on Gilead Studies GS-US-292-0104 and GS-US-292-0111), that the non-inferiority margin is 12%, and that the significance level of the test is at a one-sided 0.025 level.

This study will be conducted in accordance with the guidelines of Good Clinical Practice (GCP) including archiving of essential documents.

GLOSSARY OF ABBREVIATIONS AND DEFINITION OF TERMS

° C	degrees Celsius
° F	degrees Fahrenheit
AE	adverse event
ALT	alanine aminotransferase
ANC	absolute neutrophil counts
ARV	antiretroviral
AST	aspartate aminotransferase
AUC	area under the plasma/serum/peripheral blood mononuclear cell concentration versus time curve
BID	twice a day
BUN	blood urea nitrogen
CBC	complete blood count
CI	confidence interval
CL _{cr}	creatinine clearance

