6.5.3. Treatment Assessments (Open-Label Rollover Extension)

For purposes of study visit identification during the open-label rollover extension, study visits will be identified by the number of weeks that have elapsed between the End of Blinded Treatment Visit and the corresponding open-label study visit, and labeled with “OL” eg. Week 12 OL, Week 24 OL, etc.

All subjects participating in the open label extension phase, without regard to their blinded treatment regimen, will return for study visits at Week 12 OL and every 12 weeks thereafter for 96 weeks.

Study visits are to be completed of the protocol-specified visit date based on the End of Blinded Treatment Visit through Week 12 OL and completed \pm 6 days of the protocol-specified visit date every 12 weeks thereafter, unless otherwise specified.

The following will be performed at the Open-Label Extension Visits:

- Review of AEs and changes in concomitant medications
- Complete physical examination (**Week 48 OL, Week 96 OL**) (urogenital/anorectal exams will be performed at the discretion of the Investigator) or symptom-directed physical examination as needed
- Vital signs measurement (blood pressure, pulse, respiration rate, and temperature), including weight
- 12-lead ECG performed supine (**Week 48 OL, Week 96 OL**)
- Urine collection for the following laboratory procedures:
 - Urinalysis
 - Urine pregnancy test (females of childbearing potential only); positive urine pregnancy tests will be confirmed with a serum test. If the test is positive, the subject will be discontinued.

CCU

- Blood sample collection for the following laboratory analyses:
 - Chemistry profile: alkaline phosphatase, AST, ALT, GGT, total bilirubin, direct and indirect bilirubin, total protein, albumin, LDH, CPK, bicarbonate, BUN, calcium, chloride, creatinine, glucose, phosphorus, magnesium, potassium, sodium, uric acid, and amylase (reflex lipase testing is performed in subjects with total amylase $> 1.5 \times$ ULN). At Weeks 24, 48, 72, and 96 OL, analyses of glucose will be done as part of the fasting metabolic assessments and not as part of the chemistry profile. In addition, TSH will also be analyzed at Week 24, 48, 72 and 96 OL.

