8.1.3. Secondary Endpoint

The secondary endpoints include:

- The proportion of subjects who achieve HIV-1 RNA < 50 copies/mL at Weeks 96 and 144 as defined by the US FDA-defined snapshot algorithm
- The proportion of subjects who achieve HIV-1 RNA < 20 copies/mL at Weeks 48, 96 and 144 as defined by the US FDA-defined snapshot algorithm
- The change from baseline in log₁₀ HIV-1 RNA and CD4+ cell count at Weeks 48, 96, and 144
- The proportion of subjects who achieve HIV-1 RNA < 50 copies/mL at Weeks 48 OL and 96 OL as defined by Missing = Excluded and Missing = Failure algorithm
- The change from baseline in CD4+ cell count at Weeks 48 OL and 96 OL.

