8.5.3. Efficacy Analyses for All GS-9883/F/TAF Analysis

The following analyses will be conducted for all GS-9883/F/TAF analysis using all GS-9883/F/TAF analysis set: (1) the proportion of subjects with HIV-1 RNA < 50 copies/mL by Missing = Excluded and Missing = Failure approaches by visit, (2) the change from baseline in CD4+ Cell Count by visits, and (3) the change from baseline in CD4 % by visits. No statistical comparison will be conducted for all GS-9883/F/TAF analysis.

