3.8.2. Analysis Windows

Subject visits might not occur on protocol-specified days. Therefore, for the purpose of analysis, observations will be assigned to two different sets of analysis windows based on the following tables: the analysis windows for the randomized phase analysis are derived relative the Study Day 1 for the randomized phase analysis, while the analysis windows for the all B/F/TAF analysis are derived relative the Study Day 1 for the all B/F/TAF analysis.

The analysis windows for HIV-1 RNA, CD4+ cell count, CD4 %, hematology, chemistry, urinalysis, urine pregnancy laboratory tests, eGFR_{CG}, vital signs, and weight (if collected) are presented in [Table 3-1](#) and [Table 3-2](#) for the randomized phase analysis and the All B/F/TAF analysis separately.

Table 3-1. Analysis Windows for HIV-1 RNA, CD4+ cell count, CD4 %, HBV DNA, Hematology, Chemistry, Urinalysis, Urine Pregnancy Laboratory Tests, eGFR_{CG}, Vital Signs, and Weight for the Randomized Phase Analysis

Visit ID	Nominal Day	Lower Limit	Upper Limit
Baseline			1
Week 4	28	2	42
Week 8	56	43	70
Week 12	84	71	126
Week 24	168	127	210
Week 36	252	211	294
Week 48	336	295	378
Week 60	420	379	462
Week 72	504	463	546
Week 84	588	547	630
Week 96	672	631	714
Week 108	756	715	798
Week 120	840	799	882
Week 132	924	883	966
Week 144	1008	967	1050
Week K (K is every 12 weeks after previous visit)	K*7	(K-6)*7+1	(K+6)*7

Table 3-2. Analysis Windows for HIV-1 RNA, CD4+ cell count, CD4 %, HBV DNA, Hematology, Chemistry, Urinalysis, and Urine Pregnancy Laboratory Tests, eGFR_{CG}, Vital Signs, and Weight for the All B/F/TAF Analysis

Visit ID	B/F/TAF Group			DTG/F/TAF to B/F/TAF		
	Nominal Day	Lower Limit	Upper Limit	Nominal Day	Lower Limit	Upper Limit
Baseline			1			1
Week 4	28	2	42	NA	NA	NA
Week 8	56	43	70	NA	NA	NA
Week 12	84	71	126	84	2	126
Week 24	168	127	210	168	127	210
Week 36	252	211	294	252	211	294
Week 48	336	295	378	336	295	378
Week 60	420	379	462	420	379	462
Week 72	504	463	546	504	463	546
Week 84	588	547	630	588	547	630
Week 96	672	631	714	672	631	714
Week k	K*7	(K-6)*7+1	(K+6)*7	K*7	(K-6)*7+1	(K+6)*7

NA = Not applicable

Note: For the B/F/TAF group, Study Day 1 is the first dose date of the B/F/TAF received in the randomized phase;

Note: For the DTG/F/TAF to B/F/TAF group, Study Day 1 is the first dose date of the B/F/TAF received in the extension phase.

Note: Week k is every 12 weeks after previous visit.

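### The final SAP gives no OL Week 96 result for the randomized B/F/TAF arm, because Table 3-2 counts that arm only from its first blinded dose

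*SAP*

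**What the plan says.** **Endpoint.** Protocol 8.1.3 lists the proportion with "HIV-1 RNA < 50 copies/mL at Weeks 48 OL and 96 OL as defined by Missing = Excluded and Missing = Failure algorithm", and CD4+ change at the same two time points. SAP 6.2.1 carries both over, the virologic one as "HIV-1 RNA < 50 copies/mL at OL Week 48 and OL Week 96 as defined by Missing = Excluded and Missing = Failure algorithm". The statistical methods in the protocol synopsis also name the time points (the proportion "at Weeks 48 OL and 96 OL will be summarized, where missing HIV-1 RNA will be excluded and treated as failure, respectively") and add CD4 percentage.

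**Clock for an OL visit.** Under Protocol 6.5.3, OL visits are "identified by the number of weeks that have elapsed between the End of Blinded Treatment Visit and the corresponding open-label study visit". The same section applies the OL schedule to every participant in the extension, whichever blinded regimen they had taken.

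**Where OL Week 96 is analyzed.** Protocol 8.11 places it with the final analysis. SAP 6.2.1 says Week 48 OL was handled at an earlier interim, and then states: "In this final analysis, the last 2 secondary endpoints will be analyzed for all visits with details defined in the next section (Section 6.3").

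**Clock used in SAP 6.3.** The notes to Table 3-2 (SAP 3.8.2) give a different origin for each group: "For the B/F/TAF group, Study Day 1 is the first dose date of the B/F/TAF received in the randomized phase", but "For the DTG/F/TAF to B/F/TAF group, Study Day 1 is the first dose date of the B/F/TAF received in the extension phase". The SAP has only two sets of windows, and the other one (Table 3-1) also starts at the first randomized dose.

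**Reporting range.** SAP 6.3.2.1 runs the Missing = Failure (M=F) summary to Week 240 for the B/F/TAF group and to Week 96 for the DTG-to-B/F/TAF group. It runs the Missing = Excluded (M=E) summary to the end of study. SAP 6.3.2.2 summarizes CD4 at each visit.

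**Method text.** Protocol 8.5.3 asks for the virologic endpoint only "by Missing = Excluded and Missing = Failure approaches by visit" and sets no origin for the visit count. SAP 6.4 declares no change from the protocol's efficacy analyses.

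**The concern.** The same label means different things in the two columns of Table 3-2. Week 96 is OL Week 96 for subjects who switched from DTG + F/TAF, but blinded Week 96 for subjects randomized to B/F/TAF. Nothing in the SAP, including the programming specification in Appendix 6, restarts the count at open-label entry for the B/F/TAF arm.

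A programmer who follows the SAP exactly will therefore produce the named OL Week 96 result for the switchers but not for the arm randomized to the test product. A reader of the report could not rebuild it from the study-week columns without each subject's open-label start date.

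**Working it through.** **Inputs**

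- Window rule (SAP Table 3-2): Week K runs from day (K−6)×7+1 to day (K+6)×7.
- M=F cap for the B/F/TAF group: Week 240 (SAP 6.3.2.1).
- Nominal Week 144: day 1008, with a visit window of ±6 weeks (Protocol 6.4).
- OL visit window: ±6 days (SAP Appendix Table 2, note l).
- Open label starts only after the last subject's Week 144 visit and completion of the Week 144 analysis (Protocol 3.4), so the wait differs between subjects. Its length is not in the documents.

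**Reproducing the plan's figures.** For K = 96 the rule gives (90×7)+1 = 631 to 102×7 = 714, which matches Table 3-2. The cap equals 144 + 96 = 240 weeks, the minimum scheduled follow-up of a B/F/TAF subject who enters and completes the extension. For K = 240 the window is (234×7)+1 = **1639** to 246×7 = **1722**.

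**When OL Week 96 falls inside Week 240**

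1. Counted in elapsed weeks, the OL Week 96 visit falls on OL start day + 96×7 = OL start + 672.
2. It is inside the window if OL start ≤ 1722 − 672 = **day 1050**. That is 1050 − 1008 = **42 days** after nominal Week 144. A start on day 1051 gives day 1723, which belongs to Week 252.
3. Measured from the actual Week 144 visit (day 966 to day 1050), the permitted wait runs from 84 days down to 0.
4. Allowing ±6 days on the OL visit moves the 42 days to between 36 and 48.
5. If OL Day 1 is the first extension dose, nominal day 672 is OL start + 671 and the cutoff becomes day 1051. This one-day difference changes none of the columns below.

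**Where the visit lands for longer waits after nominal Week 144**

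| Wait (weeks) | OL start (day) | OL Week 96 (day) | Column |
|---|---|---|---|
| 12 | 1092 | 1764 | Week 252 |
| 24 | 1176 | 1848 | Week 264 |
| 36 | 1260 | 1932 | Week 276 |
| 48 | 1344 | 2016 | Week 288 |
| 60 | 1428 | 2100 | Week 300 |

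All five lie beyond the M=F cap. In the M=E and CD4 tables the values appear, but spread over several columns.

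**Illustrative share inside Week 240 (assumptions, not document figures).** Take enrolment as uniform over T weeks, Week 144 visits as on schedule, and S weeks for the Week 144 analysis plus return to clinic. A subject enrolled E weeks before the last one waits E + S weeks, so the share with a wait of at most 6 weeks is (6 − S)/T.

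| | S = 0 | S = 4 | S ≥ 6 |
|---|---|---|---|
| T = 26 | 6/26 = 23.1% | 2/26 = 7.7% | about 0% |
| T = 52 | 6/52 = 11.5% | 2/52 = 3.8% | about 0% |

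**The case against.** The strongest defence is that the SAP follows the protocol's method section. Protocol 8.5.3 sets no time origin, and Protocol 8.2.1.5 puts everyone randomized to and dosed with B/F/TAF in one group, whether or not they entered the extension. For that group, time since first B/F/TAF dose is a natural clock. Open-label entry changes no active drug for them, and an OL-indexed column would itself mix a range of exposures (Weeks 252 to 300 for the waits tabulated). The pairing of Week 240 with Week 96 in SAP 6.3.2.1 can be read as a nominal match to OL Week 96. The outputs are descriptive and involve no comparison between groups.

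Much of this stands. The study-week tables are useful and the Week 240 cap is reasonable on that scale. A subject whose OL Week 96 visit falls after the cap is not automatically counted as a failure. The problem also starts partly in the protocol, whose endpoint and synopsis name OL Weeks 48 and 96 while 8.5.3 does not.

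It does not remove the gap. The endpoint restated in SAP 6.2.1 is a value at OL Week 96. The Week 240 match holds only for short waits and is never stated as a mapping. SAP 6.4 does not say how the protocol's two descriptions are reconciled. How OL Week 48 was indexed at the interim cannot be checked, because those documents were not supplied.

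**Conclusion.** The concern holds. As written, the final SAP yields OL Week 96 estimates for the DTG-to-B/F/TAF group only. This conclusion is read directly from the SAP and needs no assumption about waiting times; only the illustrative shares do.

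The reach is limited. It affects descriptive virologic and CD4 outputs for B/F/TAF-arm subjects who entered open label, at most about 300 as planned (the actual number is not given). The primary analysis and the Week 48, 96 and 144 comparisons are untouched. It should still be corrected, because a named secondary result is missing for the arm randomized to the test product.

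**What to change.** Keep all existing tables and the Week 240 cap. Add one OL-anchored window table for B/F/TAF-arm subjects treated in the extension, with OL Day 1 as the first extension-phase dose. At OL Week 96, report:

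1. HIV-1 RNA below 50 copies/mL by M=E.
2. The same by M=F over OL-treated subjects, labelled as conditional on entering open label, since Protocol 6.5.2 bars subjects who stopped study drug earlier.
3. The same by M=F over the arm's existing All B/F/TAF denominator, labelled as counting non-entrants as failures.
4. On-treatment change in CD4+ count, from the existing SAP 3.8.1 baseline (last value on or before the first B/F/TAF dose) and not a new OL baseline.
5. The same for CD4%.

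Do the same at OL Week 48 if the interim analysis did not index it this way. State the mapping in SAP 6.2.1, and record in SAP 6.4 that the protocol's OL time points and its Section 8.5.3 method are reconciled by it. If the SAP is already final, its Section 1 provides for documenting the change in the clinical study report.

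The cost is one window table and five descriptive outputs, or ten with OL Week 48. No new data are needed: the SAP already uses extension-phase dose dates and already counts subjects treated in open label (SAP 4.1.2).

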6.3. Efficacy Endpoints for all B/F/TAF Analysis

6.3.1. Definition of the Efficacy Endpoint for all B/F/TAF analysis

The efficacy endpoints for all B/F/TAF analysis include:

- The proportion of subjects with HIV-1 RNA < 50 copies/mL by M = E and M=F approach
- The change from baseline in CD4+ Cell Count and CD4 percentage (%) by visit

The analyses for the efficacy endpoints above will be conducted based on the All B/F/TAF Analysis Set.

6.3.2. Analysis of the Efficacy Endpoints for All B/F/TAF Analysis

6.3.2.1. Analysis of the Proportion of Subjects with HIV-1 RNA < 50 copies/mL by and Missing = Excluded and Missing = Failure Approaches

The proportion of subjects with HIV-1 RNA < 50 copies/mL will be analyzed using M = E for imputing missing HIV-1 RNA values using the All B/F/TAF Analysis Set for the all B/F/TAF analysis.

- Missing = Excluded (M = E)

In this approach, all missing data will be excluded in the computation of the percentages (ie, missing data points will be excluded from both the numerator and denominator in the computation). The denominator for percentages at a visit is the number of subjects in the all B/F/TAF analysis set with nonmissing HIV-1 RNA value at that visit.

- Missing = Failure (M = F)

In this approach, all missing data will be treated as HIV-1 RNA \geq 50 copies/mL. The denominator for percentages is the number of subjects in all B/F/TAF analysis set.

For M = E and M=F analyses, the number and percentage of subjects with HIV-1 RNA in the following categories will be summarized:

- < 50 copies/mL
 - < 20 copies/mL
 - < 20 copies/mL Not Detectable
 - < 20 copies/mL Detectable
 - 20 to < 50 copies/mL

- 50 to < 200 copies/mL
- 200 to < 400 copies/mL
- 400 to < 1000 copies/mL
- ≥ 1000 copies/mL
- Missing (only applicable for M=F analysis)

For all B/F/TAF analyses, the 95% CI for the proportion of subjects with HIV-1 RNA < 50 copies/mL for a treatment group will be constructed using the Clopper-Pearson exact method.

For M =F analysis, results will be summarized by visit up to Week 240 for B/F/TAF group and up to Week 96 for DTG + F/TAF to B/F/TAF group. For the M = E analysis, results will be summarized by treatment group for all visits through the end of study. No statistical comparison will be made for the all B/F/TAF analysis.

